6.2. DATA SAFETY MONITORING BOARD

The DSMB will evaluate issues of participant safety, the adequacy and integrity of accumulating data and study's ability to test the a priori hypotheses. The DSMB will also identify if any study procedures should be altered or stopped in the event of an indication of clinical benefit or harm to participants attributable to the study interventions.

A DSMB will be convened and will be comprised of three members including a biostatistician, one psychiatrist experienced in treating patients with schizophrenia and one internist with experience with management of obesity and diabetes. No members of the DSMB will be affiliated with any of the other institutions involved in the study.

During the initial meeting of the DSMB, the Board will formulate its operating procedures, including such issues as the Board's meeting schedule; the study monitoring process; the types and formats of reports it will receive from the study statistician; and how minutes will be taken and distributed.

Before the study is opened to subject accrual, the DSMB will meet to review the study protocol, particularly the specific outcome definitions, the analysis plan, the procedures for recording and reporting SAEs, and the monitoring proposal. The subject informed consent document/process also will be inspected to ensure that all required elements have been included in language understandable to a typical study subject to be enrolled in the trial.

The DSMB will monitor and evaluate the safety of the subjects throughout the course of the research study, through the following processes:

- Assess the performance of the trial with respect to subject recruitment, retention and follow-up, protocol adherence, and data quality and completeness, to help ensure the likelihood of successful and timely trial completion.
- Monitor interim data regarding the safety of the study regimens.
- Review and consider any protocol modifications or ancillary studies proposed by the study investigators after the main trial begins to ensure that these do not negatively impact on the main trial.
- Advise the Institutional Review Board as to whether the protocol should continue as scheduled or undergo a modification due to a finding from the monitoring process.

The DSMB will meet regularly (at least twice per year) to monitor the cumulative safety data during the period when participants are in the study. The DSMB will monitor the study according to the guidelines specified in the study protocol and the operating procedures established at the initial meeting, unless the DSMB determines during the course of the trial that modification of the guidelines is in the best interest of the study and its participants. Such a decision may be based on new information that emerges during the course of the study, realization of inappropriate initial study assumptions, or the occurrence of an unanticipated scenario.

Prior to each DSMB meeting the study biostatistician will prepare a report that summarizes study enrollment, progress and all adverse events including Serious Adverse Events. This will include specific tables for adverse events related to cardiovascular, metabolic, neurological and psychiatric system organ classes.

7. STATISTICAL ANALYSES

7.1. ANALYSIS POPULATIONS

Patients who are screened but not randomized will not be included in any efficacy or safety analyses of study data. However, the number of patients screened and reasons for any screen failures will be reported. SAEs occurring during the screening period will also be reported.

7.1.1. Safety Population

The Safety Population will consist of all subjects randomized to treatment who received at least one dose of study medication. This population will form the basis for all safety analyses and selected secondary efficacy analyses.

7.1.2. Efficacy Evaluable Population

The Efficacy Evaluable Population will include all subjects in the Safety Population who completed at least one post-baseline weight measurement. This population will form the basis for the primary efficacy analyses and most secondary efficacy analyses.

7.1.3. Per-Protocol Population

The Per-Protocol Population will consist of all patients completing the 52 week assessment of weight measures and in reasonable compliance with the study protocol. This includes compliance with study medication and excludes use of a disallowed medication. This population will form the basis for selected secondary analyses.

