3.5.5. Discontinuation from Study Treatment

Study treatment MUST be immediately discontinued for the following reasons:

- Withdrawal of informed consent (subject's decision to withdraw for any reason) or if patient loses the ability to provide continued informed consent in the study
- Any clinical adverse event, clinical rating, laboratory abnormality or intercurrent illness which, in the opinion of the investigator, indicates that continued treatment with study therapy is not in the best interest of the subject
- Pregnancy
- Termination of the study

Study treatment must be reevaluated for the following reason:

- Brief Psychiatric Rating Scale total score increase by $\geq 20\%$ compared to baseline will trigger a clinical evaluation to include the site's PI. This may include the subject's regular mental health provider, as needed.

Pre-specified Discontinuation Criteria:

- 1) Subject has gained >7 kg compared to baseline weight (V0) at any visit
- 2) Subject is unwilling to continue taking study drug for any reason
- 3) Clinical Global Impression-Severity scale (CGI-S) score ≥ 6 or worsening of CGI-S score by ≥ 2 points compared to baseline
- 4) Evidence for new onset suicidal ideation, plan or evidence of self-harm based on Columbia Suicide Severity Rating Scale (C-SSRS)

- 5) eGFR <45 mL/min/1.73 m²
- 6) ALT, AST, GGT >2.5xULN (upper limit of normal), total bilirubin >1.3xULN
- 7) Serum CO₂ <19 mEq/L
- 8) Meets criteria for alcohol abuse or dependence

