7.2. STATISTICAL CONSIDERATIONS

The primary outcome is change in body weight at 52 weeks compared to baseline. The primary objective is to compare LOR/MET combination treatment with placebo. We will use a mixed model with treatment group, site and visit as factors, baseline as a quantitative covariate, and the treatment-by-visit and baseline-by-visit interaction terms. The unstructured (UN) variance/covariance matrix will be used for the analysis. The primary outcome will be a contrast examining the difference between treatment at the 52 week point for LOR/MET combination compared to placebo.

The secondary objective is to compare LOR treatment with placebo. This analysis will be performed similar to the comparison of LOR/MET combination treatment with placebo. This comparison will be declared significant if both, LOR/MET and LOR, comparisons are significant.

(We will also explore the data and calculate descriptive statistics and will use graphics, including box plots by treatment group, stem-and-leaf plots, normal probability plots, histograms and bar charts, and other graphics. In addition to the analyses above, we will perform sensitivity analyses using fasting glucose, insulin, appetite regulatory hormones, body fat distribution, smoking status, gender, and type of antipsychotic medication (low vs high liability for weight gain) as covariates in order to assess their impact on weight in this study.

We will follow the above plan for other key secondary weight and metabolic-related variables. These analyses are all exploratory. Adverse events will be tabulated by treatment arm.

7.2.1. Power and Sample Size Calculations:

Based on our preliminary data with metformin for weight loss and on the published literature with lorcaserin monotherapy (Smith et al., 2010; Fidler et al., 2011; O'Neil et al., 2012), the following weight loss is hypothesized: 1.5 kg for placebo, 4.5 kg for lorcaserin monotherapy, and 6.5 kg for lorcaserin/metformin combination. Based on the literature and on our METS trial, the standard deviation of the change scores is expected to be 6 kg. We felt that a 3 kg change would be a clinically important change, and hence, a difference between treatment groups of 3 kg (or more) in change from baseline would represent a clinically important effect. The primary contrast of

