7.2.2. Specific Aim #1

This aim will use weight measures to calculate means and standard deviations, along with their 95% confidence intervals, at each time point, along with correlations among time points.

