Appendix 2. Schedule of Events (Week 28 to End-of-Study)

Assessments	WK28 V11	WK32 V12	WK36 V13	WK40 V14	WK44 V15	WK48 V16	WK52 V17 ^a
Demographics							
Vital Signs	X	X	X	X	X	X	X
SCID/Psych + Med Hx/PE							X
Incl/Excl Criteria							
Study Drug Disp + Adherence	X	X	X	X	X	X	X
CGI – Severity	X	X	X	X	X	X	X
BPRS, C-SSRS	X	X	X	X	X	X	X
Substance Use Scale		X			X		X
Alcohol Use Questionnaire		X			X		X
Other Meds Record	X	X	X	X	X	X	X
Adverse Events/Side Effects	X	X	X	X	X	X	X
Behavioral Intervention	X	X	X	X	X	X	X
DXA (Dual X-ray absorptiometry) (UNC ONLY)						X	X*
24 hr food recall assessment, Accelerometry						X	X*
EDE-Q, TFEQ, FCI questionnaires ^c							X
LABS							
Pregnancy test ^b	X	X	X	X	X	X	X
Chemistry							X
CBC w diff							X
LFT ^d , creatinine, eGFR			X				X
Urine Drug Screen							X
Lipid Profile, HbA1c, fasting glucose							X
2hr OGTT							X
Post OGTT insulin							X
Insulin, Leptin, Ghrelin, PYY3-36, GLP-1							X

^a V17 assessments are performed at Wk52 or at any earlier visit at which a subject discontinues for any reason.

^b For female subjects of childbearing potential.

^c Eating Disorder Examination Questionnaire (EDE-Q), Three-Factor Eating Questionnaire (TFEQ), and Food Craving Inventory (FCI)

^d LFTs = AST, ALT, GGT, and total bilirubin

*DXA Scan, 24 hour food recall assessment, and accelerometry are ideally completed at Week 48 but if not done by Week 52 can be done at end of study visit.

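### The rule that stops subjects after a gain of more than 7 kg selects on the primary outcome, and the Per-Protocol set and observed week-52 means then drop those subjects, which by itself shrinks the drug-placebo differences

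*Combined protocol and SAP*

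**What the plan says.** - **Outcome.** Section 7.2: "The primary outcome is change in body weight at 52 weeks compared to baseline".
- **Stopping rule.** The first of the pre-specified discontinuation criteria in section 3.5.5 (criterion 1 below) reads: "Subject has gained >7 kg compared to baseline weight (V0) at any visit".
- **After an early stop.** The footnote to the schedule in Appendix 2 says: "V17 assessments are performed at Wk52 or at any earlier visit at which a subject discontinues for any reason". No weights are scheduled after that visit.
- **Per-Protocol set.** Section 7.1.3 requires a week-52 weight: "The Per-Protocol Population will consist of all patients completing the 52 week assessment of weight measures". It adds: "This includes compliance with study medication and excludes use of a disallowed medication". On its use: "This population will form the basis for selected secondary analyses".
- **Summaries by visit.** Section 7.2.2: "This aim will use weight measures to calculate means and standard deviations", with 95% intervals at each time point. It makes no adjustment for stopped subjects.
- **Primary analysis set.** Section 7.1.2, on the Efficacy Evaluable Population: "This population will form the basis for the primary efficacy analyses and most secondary efficacy analyses". Section 7.2 analyses weight with a mixed model with unstructured covariance and a week-52 contrast.
- **Missing data.** Section 7.2.5 promises sensitivity analyses on whether dropout is informative, but does not name them and does not mention the weight-gain rule.

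**The concern.** A subject stopped under criterion 1 has followed the protocol, yet cannot be in the Per-Protocol set unless the threshold is first passed at week 52 itself. Removal depends on a high value of the outcome. On the plan's own assumptions high values are commonest on placebo, so the placebo arm loses more of its worst outcomes than the drug arms do.

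A Per-Protocol analysis is usually read as a robustness check. Here part of any gap between it and the primary result could come from the way the set is defined. The observed placebo mean at week 52 would also show more weight loss than the arm as randomized.

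**Working it through.** **Inputs (section 7.2.1).** Expected loss 1.5 kg on placebo, 4.5 kg on lorcaserin (LOR) and 6.5 kg on lorcaserin/metformin (LOR/MET); SD of change 6 kg; two-sided 0.05; power 0.85; 27 per group; N=110 with about 25% dropout. The threshold is +7 kg (section 3.5.5).

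**The plan's own figure.** n = 2 × (1.960 + 1.036)² × 6²/5² = 25.9, so 26 by the normal approximation. With the noncentral t on two-group degrees of freedom, power is 0.838 at 26 and 0.852 at 27. The stated 27 reproduces. Dropout: 81/0.75 = 108, close to 110.

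**Closed form.** Take change as Normal(μ, 6) and a = (7 − μ)/6. The share above +7 kg is 1 − Φ(a). The mean of those kept is μ − 6φ(a)/Φ(a).

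| Arm | μ | a | Share above +7 kg | Mean of those kept |
|---|---|---|---|---|
| Placebo | −1.5 | 1.417 | 7.8% | −2.45 |
| LOR | −4.5 | 1.917 | 2.8% | −4.89 |
| LOR/MET | −6.5 | 2.250 | 1.2% | −6.69 |

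- LOR/MET-placebo: 6.69 − 2.45 = 4.24 kg, against 5.0 (15% smaller).
- LOR-placebo: 4.89 − 2.45 = 2.44 kg, against 3.0 (19% smaller, and below the plan's 3 kg threshold of clinical importance).
- Over SD 5 to 8 kg: 4.56 to 3.69 kg and 2.65 to 2.11 kg.
- Placebo subjects above +7 kg: 110/3 × 0.078 = 2.9, or 30 × 0.078 = 2.3 if 90 are randomized (the goal in section 3.2).

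**Rule applied at every visit.** The closed form ignores earlier crossings and also removes subjects who first cross at week 52, whom the plan keeps. A simulation corrects both. It uses the 17 scheduled post-baseline visits, 150,000 subjects per arm, 1 kg measurement error, week-52 SD 6 kg, and no other dropout. The mean paths and covariances are assumptions. The last column is the week-52 LOR/MET-placebo difference from a likelihood-based repeated-measures model, with the triggering weight kept in its visit slot or left out.

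| Mean path, covariance | Stopped before week 52: placebo / LOR / LOR/MET | Completers: LOR/MET-placebo | Completers: LOR-placebo | Model: kept / left out |
|---|---|---|---|---|
| Linear, random slope | 7.4 / 2.6 / 1.1% | 4.29 | 2.46 | 5.00 / 4.96 |
| Linear, Brownian | 14.0 / 6.4 / 3.6% | 4.12 | 2.38 | 5.04 / 4.72 |
| Linear, stationary type | 34.2 / 23.2 / 17.8% | 4.12 | 2.41 | 5.02 / 4.49 |
| Early plateau, random slope | 7.1 / 2.2 / 0.8% | 4.27 | 2.45 | 5.00 / 4.97 |
| Early plateau, Brownian | 12.3 / 4.2 / 1.7% | 4.03 | 2.28 | 5.02 / 4.69 |
| Early plateau, stationary type | 31.1 / 15.8 / 8.9% | 3.96 | 2.27 | 5.00 / 4.40 |

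A further run gave 4.0-4.25 and 2.2-2.4 kg, hence the overall ranges of 4.0-4.3 and 2.2-2.5 kg. Placebo supplies 58-71% of stops under random-slope or Brownian shapes and 46-56% under the stationary type, whose SD early in the trial is implausibly large. It is the largest contributor in every row.

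**Check of the remedy.** With 25% other random dropout excluded, putting criterion-1 stops back and fitting a likelihood model gave 5.07-5.13 kg (true 5.0) and 3.07-3.10 kg (true 3.0).

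**The case against.** - **The reach is limited.** This stands. A reader might infer that the primary result is biased; the documents do not support that. The primary analysis uses the Efficacy Evaluable set and a mixed model that keeps the stopped subjects' recorded weights. The Per-Protocol set serves only selected secondary analyses, and section 7.2.2 is descriptive. One condition remains: the plan does not say to which visit a discontinuation weight belongs, and calling those assessments V17 invites filing it at week 52.
- **The net direction is not fixed.** This stands too. A reader might infer that the Per-Protocol result must come out below the primary one. The arithmetic isolates one rule, but section 7.1.3 also filters on medication compliance and the plan expects about 25% dropout. As an illustration, suppose some LOR/MET subjects are non-adherent with placebo-like change, and the overall difference is held at 5.0 kg. The Per-Protocol difference is then 4.5-4.8 kg at 10% non-adherence, 4.9-5.1 at 15% and 5.2-5.4 at 20%.
- **Few subjects, modest shift.** The LOR/MET shift of 0.7-1.0 kg is about half of one standard error at 27 per arm (6 × √(2/27) = 1.63 kg). True, but it is systematic and avoidable.
- **A completer set is a common definition, and re-admitting some stops is untested.** The first part is fair. The second does not hold: the check above removes nearly all the bias even with other dropout excluded.
- **Two further over-readings.** Criterion 1 is not in the section 3.5.5 list of reasons requiring immediate discontinuation; it sits under the pre-specified criteria, so compulsory stopping is a fair reading but not the literal text. Nor is the placebo arm a picture of untreated weight gain: all arms get the behavioral program, and placebo is assumed to lose 1.5 kg.

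**Conclusion.** The concern holds for the Per-Protocol set and the observed week-52 means. Criterion 1 selects on the primary outcome, and section 7.1.3 then excludes subjects who complied with the protocol. Taken alone, this understates LOR/MET-placebo by about 0.7-1.0 kg of 5.0 and LOR-placebo by about 0.5-0.8 kg of 3.0. The figures rest on normal changes, the plan's means and SD of 6 kg, and assumed trajectories. The share stopped is much less certain than the shift: placebo about 7-14% under random-slope or Brownian shapes, up to 34% under the stationary type. The net direction of the actual Per-Protocol result cannot be predicted from the documents. The primary mixed model is largely protected; leaving the triggering weight out would give 4.4-5.0 kg in place of 5.0. This is worth correcting before unblinding, but it does not threaten the confirmatory result.

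**What to change.** Leave the clinical stopping rule as it is and change the analysis text.

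1. **Section 7.1.3:** count subjects withdrawn under criterion 1 who were otherwise compliant as per-protocol. Analyse the set with the section 7.2 mixed model, using all weights up to and including the stop visit.
2. **Section 7.2:** state that a discontinuation weight is filed at its actual study week, not as week 52. This also secures the primary analysis.
3. **Section 7.2.2:** report model-based means with 95% intervals by visit beside the observed means, label the observed means as on-treatment summaries, and tabulate criterion-1 stops by arm. Section 3.8.19 already records the reason for discontinuation.

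The cost is a few lines of SAP text and some table changes, with no new data. The downside is that the Per-Protocol set is no longer a pure completer set. With other dropout excluded, criterion-1 stops are also slightly over-represented, which overstated the differences by about 0.1 kg in simulation.

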7.2. STATISTICAL CONSIDERATIONS

The primary outcome is change in body weight at 52 weeks compared to baseline. The primary objective is to compare LOR/MET combination treatment with placebo. We will use a mixed model with treatment group, site and visit as factors, baseline as a quantitative covariate, and the treatment-by-visit and baseline-by-visit interaction terms. The unstructured (UN) variance/covariance matrix will be used for the analysis. The primary outcome will be a contrast examining the difference between treatment at the 52 week point for LOR/MET combination compared to placebo.

The secondary objective is to compare LOR treatment with placebo. This analysis will be performed similar to the comparison of LOR/MET combination treatment with placebo. This comparison will be declared significant if both, LOR/MET and LOR, comparisons are significant.

(We will also explore the data and calculate descriptive statistics and will use graphics, including box plots by treatment group, stem-and-leaf plots, normal probability plots, histograms and bar charts, and other graphics. In addition to the analyses above, we will perform sensitivity analyses using fasting glucose, insulin, appetite regulatory hormones, body fat distribution, smoking status, gender, and type of antipsychotic medication (low vs high liability for weight gain) as covariates in order to assess their impact on weight in this study.

We will follow the above plan for other key secondary weight and metabolic-related variables. These analyses are all exploratory. Adverse events will be tabulated by treatment arm.

7.2.1. Power and Sample Size Calculations:

Based on our preliminary data with metformin for weight loss and on the published literature with lorcaserin monotherapy (Smith et al., 2010; Fidler et al., 2011; O'Neil et al., 2012), the following weight loss is hypothesized: 1.5 kg for placebo, 4.5 kg for lorcaserin monotherapy, and 6.5 kg for lorcaserin/metformin combination. Based on the literature and on our METS trial, the standard deviation of the change scores is expected to be 6 kg. We felt that a 3 kg change would be a clinically important change, and hence, a difference between treatment groups of 3 kg (or more) in change from baseline would represent a clinically important effect. The primary contrast of

interest will be the difference in weight change between the placebo and lorcaserin/metformin combination treatment. Although a mixed effects model will be used for data analysis, a one-way, three-group ANOVA on change scores was used as an approximation for estimating sample size, as use of a mixed model for such estimation would have required us to hypothesize a covariance structure, pattern of dropout, and a site effect. It is thus likely that our sample size estimates are conservative. In this model, for the primary contrast of placebo versus lorcaserin/metformin combination, to achieve power=0.85, with a two-tailed significance level of 0.05, will require 27 subjects per treatment group. A sample size of N=110 will be used in order to allow for ~25% dropouts.

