diabetes and with type II diabetes (DeFronzo and Goodman, 1995; Knowler et al., 2002). Mechanisms contributing to metformin-induced weight loss are thought to include hypothalamic appetite suppression as well as slowing of gastric emptying related to stimulation of glucagon-like peptide-1 (GLP-1) secretion (Kirpichnikov et al., 2002; Mannucci et al., 2001).

Meta-analyses of studies of metformin to produce weight loss or prevent antipsychotic-induced weight gain in non-diabetic patients with schizophrenia have demonstrated mean weight loss of ~3 kg with metformin across available studies, ranging from 12-24 weeks duration (Correll et al., 2013; Mizuno et al., 2014). The study by [name] et al. (2013) demonstrated a generalizable effect of metformin on weight loss in overweight and obese non-diabetic psychiatrically stable adult outpatients with chronic schizophrenia or schizoaffective disorder.

Overweight patients with schizophrenia have been consistently found to have increased circulating leptin levels (Jin et al, 2008). Increased circulating levels of orexigenic ghrelin hormone in long-term antipsychotic treatment studies have also been found in patients who gained weight while taking antipsychotics with a high weight gain liability (Jin et al, 2008). Notably, no appetite-regulating hormones have been measured in prior studies of metformin for weight loss in schizophrenia. The current proposal will measure leptin, ghrelin (total and acylated), GLP-1 and PYY at baseline, 6 months and 12 months to gain insight into how key appetite regulatory hormones may contribute to weight loss by examining their relationships to body weight, fat distribution, and measures of appetite, energy intake and energy expenditure.

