3.9.17. Dual-Energy X-ray Absorptiometry (DXA)

DXA uses low- and high-energy photon beams to assess lean and fat tissue and bone mineral across the body. Subjects will undergo DXA scans at baseline and end-of-study. Radiation exposure from this procedure is minor, representing approximately one sixth of the unavoidable daily background radiation. DXA scanning will be conducted at the UNC site only.

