7.2.4. Specific Aim #3

The response variable is the effect of lorcaserin/metformin, LOR monotherapy and placebo on appetite regulatory hormones, body fat distribution, food intake and energy expenditure. These variable are numeric and the analyses will be similar to those performed for weight

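### Would the covariate-adjusted weight analyses in section 7.2 remove the drug effect by adjusting for the trial's own outcomes?

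*Combined protocol and SAP*

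**What the plan says.** The primary analysis in section 7.2 is a mixed model for weight with treatment, site, visit, baseline weight and two interactions with visit. The result is read from the week 52 contrast of lorcaserin/metformin against placebo. As additional work, the same section plans "sensitivity analyses using fasting glucose, insulin, appetite regulatory hormones, body fat distribution, smoking status, gender, and type of antipsychotic medication" as covariates. The reason given is to see what influence these variables have on weight. No time point is attached to them.

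Section 7.2.3 makes fasting glucose and insulin response variables for Aim 2. Section 7.2.4 does the same for Aim 3 with "appetite regulatory hormones, body fat distribution, food intake and energy expenditure". Section 2 says the hormones are measured to learn "how key appetite regulatory hormones may contribute to weight loss". On body fat, section 3.9.17 states: "DXA scanning will be conducted at the UNC site only".

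Appendices 1 and 2 schedule glucose at screening and weeks 12, 24 and 52; insulin and the hormones at screening and weeks 24 and 52; and DXA at baseline and week 48 or 52.

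**The concern.** Four of the seven listed covariates can be changed by the study drugs. If the week 52 weight contrast is adjusted for week 52 leptin or fat mass, the treatment coefficient no longer estimates the total effect. The part that travels with the covariate is taken out. A real benefit could then look as if it vanished under adjustment, and because the section calls these sensitivity analyses, a reader might take that as fragility of the primary result.

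The body-fat covariate raises a second problem whatever its time point: participants outside UNC have no DXA value, so a complete-case model drops them. Smoking status raises a third, since no visit list or schedule row names it.

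**Working it through.** **Benchmark.** The inputs from section 7.2.1 are the hypothesised losses "1.5 kg for placebo, 4.5 kg for lorcaserin monotherapy, and 6.5 kg for lorcaserin/metformin combination", so delta = 6.5 - 1.5 = 5.0 kg; "the standard deviation of the change scores is expected to be 6 kg"; "with a two-tailed significance level of 0.05"; and "to achieve power=0.85".

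- Normal approximation: n = 2 x (1.960 + 1.036)^2 x 6^2 / 5^2 = 25.9, so 26 per arm.
- Noncentral t: 26 per arm gives power 0.838 (two-group df) or 0.843 (three-group df); 27 gives 0.852 or 0.856.

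The plan's 27 per arm is reproduced. Allowing for 25% dropout, 81 / 0.75 = 108, against the planned 110.

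**Baseline covariates.** A value taken before randomisation is independent of arm in expectation, so adjusting for it leaves the expected contrast at 5.0 kg. A large simulation with SD 6 kg gave 4.99 to 5.02 kg both without adjustment and with adjustment for the baseline value.

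**On-treatment covariates.** The loss depends on the causal direction assumed.

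- The covariate carries a share p of the effect to weight. The adjusted contrast is 5 x (1 - p): 3.75, 2.5, 1.25 and 0 kg for p = 25, 50, 75 and 100%. Simulation gave 3.73, 2.48, 1.26 and 0.0.
- The covariate changes only because weight changes, M = kY + error. Its slope is r^2/k and the effect on M is k x delta, so the adjusted contrast is delta - (r^2/k)(k x delta) = 5 x (1 - r^2): 4.55, 3.75, 2.55 and 0.95 kg for r = 0.3, 0.5, 0.7 and 0.9.
- Fat mass is an example of the second case. If it follows 60% of weight change with residual SD 2 kg, r^2 = 12.96/16.96 = 0.764 and 1.18 kg remains. At 90% and residual SD 1 kg, r^2 = 29.16/30.16 = 0.967 and 0.17 kg remains.

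Every p, r and fat-mass fraction here is assumed; the documents give none.

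**Which reading fits the plan.** Weight is recorded at 17 post-baseline visits. Hormones exist at two of them (weeks 24 and 52) and DXA once, at the end. Entered as a time-varying covariate in the stated mixed model, a hormone would leave weight records at 15 of 17 visits without a matching value. Pre-treatment values fit that model unchanged, and they match both the use of baseline weight in the primary model and the presence of gender in the list. Being an outcome does not rule out a variable's own baseline as a covariate: the primary model already does this with weight.

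**DXA subset.** The UNC share is not given. For assumed shares of the 90 to be randomised (section 3.2), n per arm = 90 x share / 3, with power for 5 kg and SD 6 kg from the noncentral t (three-group df):

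| UNC share | n per arm | Power | Power after 25% dropout |
|---|---|---|---|
| 25% | 7.5 | 0.34 | 0.26 |
| 40% | 12 | 0.51 | 0.40 |
| 50% | 15 | 0.61 | 0.48 |
| 60% | 18 | 0.69 | 0.56 |
| All sites | 30 | 0.89 | 0.79 |

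The 95% half-width, t x 6 x sqrt(2/n), is 6.5 kg at 7.5 per arm, 4.4 kg at 15 and 3.1 kg at 30.

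**Smoking.** Section 3.8.2 collects demographic and medical data, and Appendix 1 has a demographics row. Neither is itemised, and gender is not named there either. Absence from the lists does not show that smoking goes unrecorded.

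**The case for a change.** The best case for a change starts from the silence on timing. The primary model specifies baseline for weight, and the same section omits it for these covariates. Section 2 describes a mechanistic interest in hormones measured at 6 and 12 months, so an analyst could follow the text and adjust for on-treatment values. Section 7.2.5 uses the term sensitivity analysis for the effect of missing data on results, which is a robustness meaning, so a reader could carry it over. The sentence in section 7.2 that calls analyses exploratory follows the one about secondary variables and may not reach back to these. If the adjusted figure fell to 2.55 or 0.95 kg, it would lie below the 3 kg that section 7.2.1 regards as clinically important.

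Two parts of this stand: the time point is unwritten, and any DXA model is a UNC subset even with baseline values. The rest does not carry through to the trial's conclusion. The stated purpose is to describe how these variables relate to weight, which is an association question. An on-treatment analysis would be a legitimate, if loosely labelled, answer to it. Nothing in the plan treats the outcome of these models as a test of the primary result. The one-site restriction is disclosed in section 3.9.17 and both schedules. The 0.85 power was set for the primary contrast, so low power in a supplementary subset model is not a design failure.

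**Conclusion.** The concern does not call for a change. That these analyses would remove the drug effect is not established: it is true only for on-treatment covariates, and the size of the loss rests on assumed correlations or mediated shares. With screening or baseline values, which are scheduled for all four variables in question, the expected contrast remains 5.0 kg.

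What remains is an unstated covariate time point and an unlabelled single-site subset for one of seven covariates. A competent analyst would use pre-treatment values in adjusted treatment comparisons, describe on-treatment relations as associations, and show the reduced sample size of any DXA model. The primary contrast and the rule for the lorcaserin comparison do not depend on these models, so spelling this out would alter no planned conclusion. This view assumes that the adjusted models are reported as supplementary, as section 7.2 places them.
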